3.2 Flow Chart

	V1 Screening & treatment start					V2	V3	V4	V5 (EOS)	
	Day -7					Day 0	Day 7	Day 14	Day 28	
	moment 0	h 1	h 2	h 4	h 8	h 12				
ICF	x									
Incusion/Exclusion criteria check	x									
Vital signs	x	x	x	x	x	x	x	x	x	x
Physical examination	x						x	x	x	x
Medical history	x									
Concomitant medication	x						x	x	x	x
Blood sampling	x	x	x	x	x	x	x	x	x	x
CoQ10 intake	x						AB	AB	AB	AB
Pharmacokinetics		x	x	x	x	x	x	x	x	x
Adverse events		x	x	x	x	x	x	x	x	x

	Study Title	Bioavailability Study of COQUN ORAL FORMULATION (CoQ10) administered in Healthy Adults (CoQ10-01)		
	Study ID	VF-BAQ10/2018	Sponsor:	VISUFARMA SpA
	Date	March 03, 2018	Vers.	Final

	Date	March 03, 2018	Vers.	Final

5 LIST OF ABBREVIATIONS AND DEFINITION OF TERMS

AE	Adverse Events
AST	Aspartate aminotransferase/glutamic oxaloacetic transaminase/GOT
AUC	Area under the concentration-time curve
AUC _{0-t}	Area under the serum concentration versus time curve to the last measurable concentration (t)
AUC _{0-inf}	Area under the serum concentration versus time curve to infinity
C _{max}	Maximum measured serum concentration
C _{min}	Concentration at the end of a dosing interval
CFR	Code of Federal Regulations
°C	Degrees Celsius
CRO	Contract Research Organization
CTR	Clinical Study Report
CRF	Case Report Form
ECG	Electrocardiogram
e.g.	Exempligratia, for example
GCP	Good Clinical Practice
ICH	International Conference on Harmonization
i.e.	Id est, that is
IEC	Independent Ethics Committee
IP	Investigational Product
IRB	Institutional Review Board
ITT	Intention-to-treat
kg	Kilogram
MedDRA	Medical Dictionary or Regulatory Activities
mg	Milligram
ug/ml	Microgram/Milliliter
PD	Pharmacodynamic
PK	Pharmacokinetic
QA	Quality assurance
QC	Quality control
PP	Per Protocol
SAE	Serious Adverse Event
SAS	Statistical Analysis System (SAS [®])
SOP	Standard operating procedure
SUSAR	Suspected Unexpected Serious Adverse Reaction
t _{1/2}	Apparent terminal elimination half-life
t _{max}	Time of the maximum measured serum concentration
TMF	Study Master File

	Study Title	Bioavailability Study of COQUN ORAL FORMULATION (CoQ10) administered in Healthy Adults (CoQ10-01)		
	Study ID	VF-BAQ10/2018	Sponsor:	VISUFARMA SpA
	Date	March 03, 2018	Vers.	Final

6 INTRODUCTION

6.1 Background

Coenzyme Q10 (CoQ10) is a substance similar to a vitamin. It is found in every cell of the body. The body produces CoQ10, and the cells use it to produce energy for the body needs for cell growth and maintenance. It also functions as an antioxidant, which protects the body from damage caused by harmful molecules. CoQ10 is naturally present in small amounts in a wide variety of foods, but levels are particularly high in organ meats such as heart, liver, and kidney, as well as beef, soy oil, sardines, mackerel, and peanuts.

The Coenzyme Q10, also known as ubiquinone, is an endogenous molecule, synthesized by our body and essential for the proper functioning of the mitochondria, or the cellular units responsible for the production of energy in the body.

In organisms it participates in redox reactions and, depending on the state of oxidation, it can be present in three forms: an oxidized, a semi-quinone intermediate and a reduced form. The side chains make it very lipophilic, in fact it is present in biological membranes, especially mitochondrial ones.

Higher levels of Q10 could improve the efficiency of the electron transport chain, increasing the available energy.

Rebalancing the function of the mitochondria, which are in practice the "lungs" of every single cell, means allowing the cell to restore its original energy potential, and, in a certain sense, to "rejuvenate" allowing it to "breathe" and use the available energy correctly.

If coenzyme Q is reduced by acquiring an electron it forms a radical called ubisemichinone (QH.). For further reduction the compound becomes a ubiquinol (QH2).

The concentration of coenzyme Q10 tends to decrease with aging; low levels are also recorded in the presence of particular chronic diseases, such as those resulting from heart problems, Parkinson's disease, muscular dystrophy, diabetes, cancer and AIDS. Certain drugs, such as statins used in the control of hypercholesterolemia, can also lower Coenzyme Q10 levels.

Coenzyme Q10 has been shown to have beneficial effects on some patients with migraine and is a major component of the myth cocktail used in the treatment of mitochondrial myopathy and other metabolic disorders.

Taking 100 mg a day or more of CoQ10 has caused mild insomnia in some people. And research has detected elevated levels of liver enzymes in people taking doses of 300 mg per day for long periods of time. Liver toxicity has not been reported.

Other reported side effects include rashes, nausea, upper abdominal pain, dizziness, sensitivity to light, irritability, headache, heartburn, and fatigue.

Medicines for high cholesterol (statins) and medicines that lower blood sugar cause a decrease of CoQ10 levels and reduce the effects of CoQ10 supplements. CoQ10 can reduce

	Study Title	Bioavailability Study of COQUN ORAL FORMULATION (CoQ10) administered in Healthy Adults (CoQ10-01)		
	Study ID	VF-BAQ10/2018	Sponsor:	VISUFARMA SpA
	Date	March 03, 2018	Vers.	Final

the body's response to the blood thinner (anticoagulant) medicine warfarin (Coumadin) and can decrease insulin requirements in people with diabetes.

Many factors can affect the Q10 blood level of people who are not taking a Q10 supplement: age, diet, disease, medications (for example, statin medications).

Q10 levels in the blood from the body's own synthesis of the substance increase after (0.20 ug/ml) birth until about the age of 21. Thereafter, the body's synthesis of Q10 gradually decreases.

It is expected that supplementing regularly with Q10 to raise the Q10 blood level, but much depends on the way in which the Q10 product has been prepared and much depends on the dosage. It was demonstrated that taking 30 milligrams or 50 milligrams of Q10 daily will not raise the Q10 level as much as taking 100 mg of Q10 daily will do, while taking 100 milligrams of Q10 twice daily will yield even greater gains in Q10 blood levels.

From the literature it is known that a well-absorbed Q10 supplement should over time raise the blood level to about 2.5 micrograms per milliliter if the individual is taking a 100-milligram dosage once a day, while if taken the same Q10 supplement in a dosage of 100 milligrams twice a day, its blood level should, over time, raise the steady-state Q10 blood level to somewhere in the area of 3.5 micrograms per milliliter. But, the attainable levels will vary from individual to individual, beside depending on the product itself as formulation.

Recent studies have shown how the antioxidant effects of the enzyme Q10 can have benefits on the body and on the brain. Some of these studies indicate that coenzyme Q10 can protect the brain from neurodegenerative diseases, such as Parkinson's disease, as well as damage that causes ischemia (stroke) to the brain. Other recent studies show a benefit regarding the possibility of survival, after cardiac arrest, if coenzyme Q10 is given concurrently to a cooling of body temperature (between 32-34 degrees Celsius).

The endogenous concentrations of Coenzyme Q10 tend to reduce also in the presence of some chronic neurodegenerative diseases, such as Glaucoma.

Numerous scientific studies have shown that the axons of retinal ganglion cells are rich in mitochondria necessary to produce energy for nerve conduction. The reduction in energy production and the increase in the production of mitochondrial free radicals of ganglion cells is to be considered a key mechanism in the etiopathogenesis of glaucoma, which predisposes to the death of such cells and their axons.

Recent studies have also shown that CoQ10 ameliorates oxidative stress in ischemic retina, promotes retinal ganglion cell (RGC) survival in ischemic retina induced by intraocular pressure elevation and apoptotic cell death by decreasing Bax or by increasing pBad protein expression in ischemic retina, providing a promising therapeutic potential for ameliorating oxidative stress-mediated mitochondrial dysfunction in ischemic retinal injury.

	Study Title	Bioavailability Study of COQUN ORAL FORMULATION (CoQ10) administered in Healthy Adults (CoQ10-01)		
	Study ID	VF-BAQ10/2018	Sponsor:	VISUFARMA SpA
	Date	March 03, 2018	Vers.	Final

Also, topical CoQ10 appears an effective therapy preventing RGC apoptosis and loss in glaucoma-related models.

6.2 Rationale of the Study

Many studies showed the beneficial proprieties of CoQ10 on the body and on the brain especially if taken on a daily basis, as well as its properties to ameliorate oxidative stress in ischemic retina, providing a promising therapeutic potential for ameliorating oxidative stress-mediated mitochondrial dysfunction in ischemic retinal injury and for preventing RGC apoptosis and loss in glaucoma-related models.

It is expected that supplementing regularly with Q10 will raise the Q10 blood level, but much depends on the way in which the Q10 product has been prepared and much depends on the dosage. It was demonstrated that taking 30 milligrams or 50 milligrams of Q10 daily will not raise the Q10 level as much as taking 100 mg of Q10 daily will do, while taking 100 milligrams of Q10 twice daily will yield even greater gains in Q10 blood levels.

From the literature it is known that a well-absorbed Q10 supplement should over time raise the blood level to about 2.5 micrograms per milliliter if the individual is taking a 100-milligram dosage once a day, while if taken the same Q10 supplement in a dosage of 100 milligrams twice a day, its blood level should, over time, raise the steady-state Q10 blood level to somewhere in the area of 3.5 micrograms per milliliter. But, the attainable levels will vary from individual to individual, beside depending on the product itself as formulation.

Therefore, this bioavailability study is intended to be performed in order to evaluate the best dosage for COQUN ORAL FORMULATION, with its innovative technology based on the modified release of active principles at certain time intervals, in order to reach a level of plasma concentration which might assure its antioxidant effect if taken on a regular daily basis.

6.3 Risk/Benefit Consideration

Taking 100 mg a day or more of CoQ10 has caused mild insomnia in some people and research has detected elevated levels of liver enzymes in people taking doses of 300 mg per day for long periods of time. Liver toxicity has not been reported.

Other reported side effects include rashes, nausea, upper abdominal pain, dizziness, sensitivity to light, irritability, headache, heartburn, and fatigue.

Medicines for high cholesterol (statins) and medicines that lower blood sugar cause a decrease of CoQ10 levels and reduce the effects of CoQ10 supplements. CoQ10 can reduce the body's response to the blood thinner (anticoagulant) medicine warfarin (Coumadin) and can decrease insulin requirements in people with diabetes.

Many factors can affect the Q10 blood level of people who are not taking a Q10 supplement: age, diet, disease, medications (for example, statin medications).

	Study Title	Bioavailability Study of COQUN ORAL FORMULATION (CoQ10) administered in Healthy Adults (CoQ10-01)		
	Study ID	VF-BAQ10/2018	Sponsor:	VISUFARMA SpA
	Date	March 03, 2018	Vers.	Final

For this study, the subjects will be screened in order to be healthy, with no concomitant diseases, who will receive 100mg or 200mg of COQUN ORAL FORMULATION for 1 month and will be treated appropriately and constantly monitored so that benefits outweigh potential risks for the subjects.

7 STUDY OBJECTIVES AND VARIABLES

7.1 OBJECTIVES

Primary objective:

The primary objective of this study is to evaluate the best dosage between 100mg OD or 100mg BID for COQUN ORAL FORMULATION in order to reach a level of plasma concentration which might assure its antioxidant effect if taken on a regular basis.

Secondary Objectives:

Secondary objectives of this study are:

- To evaluate the safety and tolerability COQUN ORAL FORMULATION following single dose of 100mg
- To evaluate the safety and tolerability of COQUN ORAL FORMULATION during the 1 month daily dose

7.2 VARIABLES

Primary Variable

Pharmacokinetic properties:

- Area under the curve (microg/ml x h): ≥ 5
- Cmax: $\geq 0,8$
- Tmax: ≥ 3
- elimination half-life (t 1/2)

Secondary Variable(s)

The secondary variables are the ones regarding safety which will be monitored through vital signs, physical exams, ECGs, clinical laboratory tests and adverse events, as follows:

- following a single oral dose of 100mg COQUN ORAL FORMULATION
- in 1 month period of daily oral intake of 100mg OD or BID COQUN ORAL FORMULATION

Symptoms and signs like mild insomnia, elevated levels of liver enzymes, rash, nausea, upper abdominal pain, dizziness, sensitivity to light, irritability, headache, heartburn, and fatigue will be closely monitored.

8 SUBJECT POPULATION

8.1 Subject Population

	Study Title	Bioavailability Study of COQUN ORAL FORMULATION (CoQ10) administered in Healthy Adults (CoQ10-01)		
	Study ID	VF-BAQ10/2018	Sponsor:	VISUFARMA SpA
	Date	March 03, 2018	Vers.	Final

In order to participate in this study, each subject must meet all of the following inclusion and none of the exclusion criteria at screening and at check-in.

24 subjects will be screened in order to receive a single dose of 100mg COQUN ORAL FORMULATION, while after 1 week of wash-out period, the subjects will be divided in two equal groups of 12 subjects each in order to enter the 1 month multidose phase: group A (12 subjects) will receive 100mg OD of COQUN ORAL FORMULATION, while the group B (12 subjects) will receive 100mg BID of COQUN ORAL FORMULATION.

8.2 Inclusion Criteria

Subjects will only be included in the study if they meet all of the following criteria:

- Subject Informed consent form (ICF) is signed
- M & F Aged between 35-75 years at the time of the signature of ICF
- A body mass index between 20 and 29 kg/m²
- Fasting the night before enrolment, for at least 10 hours
- Healthy, meaning absence of any prescribed medication for a month prior to the inclusion to the study and during the study
- Willing to avoid a consumption of any food supplements except vitamin D and calcium at least 2 weeks before and during the study
- Consumption of dairy and cereal products (standardized breakfast will include low lactose dairy and bread)
- Willing to follow all study procedures, including attending all site visits (including sessions during which a venous line will be inserted for blood sampling), and keeping a diary for the time of multiple-dose study (to follow their compliance and palatability)

8.3 Exclusion Criteria

Subjects will not be included in the study if any of the following criteria applies:

- Intake of any prescribed medication within 2 weeks of the beginning of the study
- Intake of any food supplements within 2 weeks of the beginning of the study, except vitamin D and calcium
- Hypotension
- Any clinically significant history of serious digestive tract, liver, kidney, cardiovascular or hematological disease, diabetes
- Gastrointestinal disorders or other serious acute or chronic diseases
- Known lactose/gluten intolerances/ food allergies (limitation for standardization of meals)
- Inadequate veins (in the opinion of the investigator) or known contraindication to placement of a dedicated peripheral line for venous blood withdrawal
- Known drug and/or alcohol abuse
- Using any form of nicotine or tobacco
- Mental incapacity that precludes adequate understanding or cooperation
- Participation in another investigational study or blood donation within 3 months prior to or during this study

	Study Title	Bioavailability Study of COQUN ORAL FORMULATION (CoQ10) administered in Healthy Adults (CoQ10-01)		
	Study ID	VF-BAQ10/2018	Sponsor:	VISUFARMA SpA
	Date	March 03, 2018	Vers.	Final

8.4 Premature Discontinuation

Any subject who discontinued the study before the scheduled completion of the study procedures will be considered as prematurely discontinuation, regardless of the reason for discontinuation.

Upon discontinuation, the final study visit should be performed. For safety reasons, reasonable attempt should be made to contact withdrawn subjects in due time post the discontinuation to gather information on adverse events and long-term outcome measures, i.e. laboratory measurements. Information collected as a result should be recorded on the appropriate CRF pages.

Drop-outs, if any, will be replaced only if the per-protocol number of subjects will not be reached in order to have the per-protocol number of subjects.

8.4.1 Premature Discontinuation due to an Adverse Event

Adverse events resulting premature discontinuation of a subject must be assessed, documented, and reported by the investigator as per protocol (see section 11.1.6). Subjects that are withdrawn due to an adverse event not resolved by end of study visit should be followed up until the event or its sequel resolves or stabilizes at a level acceptable to the investigator and the sponsor.

8.4.2 Premature Discontinuation by the Subject

Subjects may discontinue the study at any time without giving reasons and without any disadvantageous consequences for their subsequent medical care.

8.4.3 Premature Discontinuation of a Subject by the Investigator

The investigator may withdraw a subject from the study at any time in case of intercurrent illness, adverse event, and therapeutic procedure or as a general rule if further participation in the study is believed to be to the subject's detriment.

The investigator must immediately withdraw any subject from the study who is found not to be eligible for the study based on the inclusion and exclusion criteria. This can occur, for example, in the case of alarming examination results or strikingly abnormal laboratory values. In these cases, no investigational product is to be administered and no protocol procedures are to be performed any more.

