9.8 Previous and Concomitant Medication

Any medication taken in parallel with the IP is defined as concomitant medication and will be carefully documented in the CRF including the previous medication administered within the last 2 months prior to the start of the study.

Except for medication which may be required to treat AEs (see below), no medication will be allowed during the entire study duration, in concomitance with the IP until after the end-of-study evaluation.

The investigator will instruct the subject to notify the study site about any new medications or significant non-drug therapies (including physical therapy and blood transfusions) administered after the start of the IP. All such medications and non-drug therapies will be documented in the CRF and may require the subject to be withdrawn.

Whenever possible, administration of concomitant medication should be avoided with special attention to PK and PD sampling and may require the subject to be withdrawn.

For previous and concomitant medication/therapy the following information will be recorded in the CRF:

- Brand name or generic name (preferred)
- Indication
- Total daily dose and units
- Route of administration
- Time/duration of treatment.

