10.7 Premature Termination of the Study

The subject may withdraw from the study any time without giving reasons and without any disadvantageous consequences for his subsequent medical care. Furthermore, the subject should be withdrawn from the study if the investigator has the impression that it would be to the subject's detriment to continue the study.

In case of premature termination from the study the investigator should perform the following:

- physical examination
- vital signs (blood pressure, heart rate temperature and respiratory rate)
- body measurements (weight)

	Study Title	Bioavailability Study of COQUN ORAL FORMULATION (CoQ10) administered in Healthy Adults (CoQ10-01)		
	Study ID	VF-BAQ10/2018	Sponsor:	VISUFARMA SpA
	Date	March 03, 2018	Vers.	Final

- 12 lead ECG
- blood laboratory analysis (Hematology,) to be performed at investigator discretion whenever indicated by the subject health status
- record of concomitant medication
- adverse events

Note: If the subject did not receive any IP (i.e., premature termination between the ICF signature and the single dose phase) no further examination are necessary to be performed and subject will be declared screening failure.

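### Protocol 8.4.3 stops all procedures for any subject found ineligible, dosed or not, which contradicts the final visit in 8.4 and the exit assessments in 10.7 (minor)

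*Protocol*

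**What the plan says.** Protocol 8.4.3 has two parts. The first lets the investigator withdraw a subject for illness, an adverse event or the subject's own good. The second makes withdrawal immediate and mandatory for any subject who turns out not to meet the eligibility criteria, with worrying examination or laboratory findings as examples. It ends with the instruction that "no investigational product is to be administered and no protocol procedures are to be performed any more".

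Two other sections deal with leaving early:

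- Section 8.4 treats every early exit alike, whatever the reason: "Upon discontinuation, the final study visit should be performed". It also asks for an attempt to contact withdrawn subjects "to gather information on adverse events and long-term outcome measures, i.e. laboratory measurements".
- Section 10.7 says: "In case of premature termination from the study the investigator should perform the following". The list covers physical examination, vital signs, weight, 12-lead ECG, blood tests at the investigator's discretion, concomitant medication and adverse events. A note waives these for subjects who took no product and classes them as screening failures.

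On timing, 8.1 requires subjects to meet "none of the exclusion criteria at screening and at check-in". Two criteria nevertheless extend into the treatment period. One exclusion in 8.3 is "Participation in another investigational study or blood donation within 3 months prior to or during this study". One inclusion criterion in 8.2 is "absence of any prescribed medication for a month prior to the inclusion to the study and during the study". On other treatment taken after the start of the product, 9.8 says: "All such medications and non-drug therapies will be documented in the CRF and may require the subject to be withdrawn".

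**The concern.** The note in 10.7 shows where the protocol means to draw the line: at the first dose. Someone who never took the product needs no exit examination; someone who did should have one. The last sentence of 8.4.3 ignores that line. It is also worded as an obligation, whereas 8.4 and 10.7 say only what should be done, so a site trying to reconcile the three could reasonably follow 8.4.3.

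At stake is the exit safety check on an exposed healthy volunteer. Safety and tolerability after the single dose and during the month of daily dosing are the secondary objectives (protocol 7.1), and ECGs are among the secondary variables in 7.2. Section 10.6.7 schedules ECGs only at screening and at end of study, so a dosed subject handled under 8.4.3 would have none after taking the product.

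**Working it through.** There is no planned figure to reproduce. The check compares the sections and then counts what one affected subject would lose.

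**1. What each section requires when a subject is found ineligible**

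| | No product taken | Product taken |
|---|---|---|
| 8.4.3 | No product, no procedures | No product, no procedures |
| 8.4 | Final visit | Final visit |
| 10.7 | Waived; screening failure | Exit assessments |

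For an undosed subject, the 10.7 note settles the matter and agrees with 8.4.3. For a dosed subject, 8.4.3 disagrees with both other sections.

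**2. Can a dosed subject be found ineligible?**

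- *Another study or blood donation (8.3).* The criterion expressly covers the period of this study. A volunteer who gives blood on, say, Day 10 meets an exclusion criterion and has already been dosed. This is the clearest route.
- *Prescribed medication (8.2).* This also covers the study period, but it is a weaker route: 9.8 permits treatment of adverse events and makes withdrawal for other medication a possibility, not a certainty.
- *Late discovery.* Sections 9.6 and 10.5.1 place eligibility before the V1 dose, so learning of ineligibility after V1 departs from the planned order. The SAP passage on inclusion and exclusion criteria (after 5.1.4) does have the criteria checked again at Visit 2, by which time every subject has had the V1 dose. However, the protocol flow chart (3.2) and SAP 5.1.1 place the check at Visit 1 only. The finding does not depend on this route.

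**3. What is lost per affected dosed subject**

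- Exit items in 10.7: physical examination, vital signs, weight, ECG, concomitant medication, adverse events = 6 unconditional; blood tests = 1 discretionary; 6 + 1 = 7.
- ECGs after the product (10.6.7, 10.7): 0 if 8.4.3 is followed, 1 if 10.7 is followed.

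**4. Exposure since the last scheduled check, multidose phase**

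Visits fall on Days 0, 7, 14 and 28 (10.6.14). The gaps are 7 − 0 = 7, 14 − 7 = 7 and 28 − 14 = 14 days, so the longest is 14 days.

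- Once daily: 14 × 1 = 14 capsules; 14 × 100 mg = 1,400 mg.
- Twice daily: 14 × 2 = 28 capsules; 28 × 100 mg = 2,800 mg.

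The upper bound on total intake, counting the V1 capsule and 28 dosing days taken in full, is:

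- Once daily: 1 + 28 × 1 = 29 capsules = 2,900 mg.
- Twice daily: 1 + 28 × 2 = 57 capsules = 5,700 mg.

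These totals describe how much product an unexamined subject may have taken. They do not measure harm.

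**5. What still applies under 8.4.3**

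Follow-up of adverse events (11.1.5, 11.1.6.1), serious adverse event reporting (11.1.6.2) and the contact attempt in 8.4, which names laboratory measurements.

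**The case against.** The best defence is that 8.4.3 was written for screening. Its examples fit that stage, 8.1 ties the criteria to screening and check-in, and after screening an alarming laboratory value becomes an adverse event under 11.1.1, so that subject leaves under 8.4.1 and 10.7. Breaches during treatment are handled elsewhere: SAP 5.1.3 treats disallowed medication as a protocol violation, judged case by case. On this reading, 8.4.3 ends participation and 10.7 governs the exit.

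This is a plausible account of the intention, and it narrows the finding: the abnormal-result examples should not be used to argue that the problem is common or serious. It does not cure the text. The sentence covers every subject found ineligible, sets no time limit, and stops procedures without referring to 10.7. Blood donation or joining another study after dosing remains squarely within it.

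A second objection is that the ECG loss is overstated. The flow chart has no ECG row, the V5 list in 10.5.3 omits it, and SAP 5.2.2 names only vital signs and adverse events as secondary variables. That is fair as a comment on how inconsistently the ECG is planned. Even so, 10.6.7 calls for one at end of study and 10.7 calls for one at early exit, and the other five unconditional items do not depend on it.

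A third objection is that the 8.4 final visit could mean V5 in full, including pharmacokinetic sampling, so that a fix based on 10.7 would leave a smaller mismatch. It is reasonable to take 10.7 as defining the content of an early exit visit, but the rewording should say so.

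**Conclusion.** The contradiction is real, and 8.4.3 is wrong as worded for a subject who has taken the product. It is minor. Undosed subjects are unaffected. The documents give no frequency for the dosed case, and it should be rare. Per affected subject, the loss is up to seven exit items, including the one ECG after intake, at a point where the last scheduled visit may be up to 14 days back. The remaining safety duties limit the consequence, and no effect on the planned analysis is claimed.

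This assumes that a site would follow the mandatory sentence literally, that the procedures it stops include the 10.7 assessments, and that a breach of a criterion continuing into the study counts as being found ineligible. Someone who reads 8.4.3 as applying only before dosing would not reach the same result in practice, but would still have reason to put that limit into the text.

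**What to change.** Replace the last sentence of 8.4.3 with wording to this effect:

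- No further product is given to a subject found ineligible.
- If no product has been taken, no further procedures are done and the subject is recorded as a screening failure, as in the 10.7 note.
- If any product has been taken, pharmacokinetic and pharmacodynamic procedures stop, but the 10.7 exit safety assessments are carried out and adverse events are followed up. In this case the 10.7 list constitutes the final visit required by 8.4.

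The change follows the line the protocol already draws at dosing and adds no new assessment. It costs one protocol sentence and one exit visit in a rare case.
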